3.2 Secondary objectives

- To evaluate the local and systemic safety profile with the different routes of administration.
- To determine the feasibility of measuring tranexamic acid in dry blood spots

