4.1.2 Secondary endpoints

- Average pain score and duration of pain after administration (visual analogue scale) for each administration route at visits V1, V3, V5
- Reaction at site of injection (redness, swelling, induration, tenderness, ecchymosis, necrosis, nerve injury, infection) for IM and IV administration route at visits V1, V2, V3, V4, V5, V6,
- Vital signs (blood pressure, heart rate and respiratory rate) after administration for each administration route at visits V1, V2, V3, V4, V5, V6
- Solicited adverse events (fever, nausea, vomiting, diarrhoea, visual impairment, seizure)
- Number of participants with solicited local and systemic adverse events
- Number of participants reporting one or more adverse events and serious adverse events
- Correlation between serum and dry blood spot concentrations for each administration route at visits V1, V3, V5

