5.2 Inclusion visit (V1)

All **inclusion and exclusion criteria** have to be checked by physician, to ensure laboratory tests done at the screening visit are within normal values and for women, the pregnancy test is negative.

If a volunteer meets all inclusion and has no exclusion criteria and s/he consents to participate, the participant is considered **enrolled**. The investigator will randomize her/him to one of six groups (see Section 4.2.1).

Visit V1 (=1st drug administration):

- All women must have a **pregnancy test** (urine β hCG) done which must be negative to continue this visit.
- Participants medical history will be checked to ensure there are no changes since V0 visit.
- Baseline blood pressure, heart rate and respiratory rate will be recorded
- T₋₁: One blood sample will be taken for pharmacokinetics immediately prior to drug administration (0,5 mL venous blood taken in a dry tube without anti-coagulant)

- T₀: Drug Administration (PO, IV or IM) (as per randomization)
- **Pain assessment** using a Visual Analogue Scale (VAS) will be recorded immediately after drug administration and at 2 hourly intervals up to 8 hours. The VAS used will be the Numerical Pain Rating Scale where individuals rate their pain on a ten-point numerical scale. The scale is composed of 0 (no pain at all) to 9 (worst imaginable pain). The duration of any pain associated with IV or IM administration will be assessed once at 8 hours. Participants will be offered pain relief if needed in the form of simple analgesia (paracetamol).
The duration of any pain associated with IV or IM administration will be assessed once at 8 hours.
- Blood samples for **pharmacokinetics** (*0,5 mL of venous blood in dry tube without anti-coagulant*) will be taken at the following times after drug administration:
 - T₀+ 5min (only for IV route)
 - T₀+30min
 - T₀+1h
 - T₀+2h
 - T₀+3h
 - T₀+4h
 - T₀+5h
 - T₀+6h
 - T₀+8h (only for IM and PO routes)
- **Dry Blood Spot:** At one time-point (any time-point between T₀+ 5min and T₀+8h), a capillary blood sample will be taken at a finger with a lancet and a drop of blood will be placed on Mitra[®] device. An aliquot of 200µL of whole blood will be taken and aliquoted from the venous blood sample taken at the same time.

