- All the **adverse events** and **concomitant treatments** will be recorded.

Visit V6 (=visit V5 +24h):

- **Pain assessment** using a Visual Analog Scale will be recorded at T₀+24h (+/- 1 hour). The VAS used will be the Numerical Pain Rating Scale where individuals rate their pain on a ten-point numerical scale. The scale is composed of 0 (no pain at all) to 9 (worst imaginable pain). Participants will be offered pain relief if needed in the form of simple analgesia (paracetamol).
- **Vital signs** (blood pressure, heart rate and respiratory rate) recorded at T₀+24h (+/- 1 hour).
- Blood samples for **pharmacokinetics** (*0,5 mL of venous blood in dry tube without anti-coagulant*) will be taken at T₀+24h.
- **Reaction at site of injection:** Each injection site will be checked visually for local reaction and any other complications (including redness, swelling, induration, tenderness, ecchymosis, necrosis, nerve injury, infection) at T₀+24h (+/- 1 hour). Reaction will be measured in millimetre, and time of occurrence will be recorded.
- All the **adverse events** and **concomitant treatments** are collected.
- **Laboratory tests:**
 - Haematology tests (full blood count)
 - Renal function test (urea, creatinine and GFR)
 - Coagulation tests (fibrinogen, D-dimers, prothrombin time and partial thromboplastin time)
 - For women: pregnancy test (urine βhCG)

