5.7 Biological samples

5.8.1 Pharmacokinetics study

Serum PK samples: each dosage requires 0,5 ml of blood in dry tube without anticoagulant. The PK sample will then be centrifuged for 10 min at 4 000 rpm then the serum will be frozen at -20°C

The samples will be kept frozen at -20°C in the Clinical Investigation Centre of Necker Hospital. Once all the samples have been collected, they will be sent frozen to the mass spectrometry platform of the UFR Sciences de la Santé Simone Veil, University Versailles Saint Quentin, [name], France to perform the analysis under the supervision of [name].

Dry Blood Spot: for each participant, at visit 1, 3 and 5, at one time-point (any time-point between T0+ 5min and T0+8h), a capillary blood sample will be taken at a finger with a lancet and a drop of blood will be placed on Mitra® device. An aliquot of 200µL of whole blood will be taken and aliquoted from the venous blood sample taken at the same time. The filter papers will be kept at ambient temperature in the Clinical Investigation Centre of Necker Hospital during the study period. Once all the samples have been collected, they will be sent in the same time than serum PK samples to the UFR Sciences de la Santé Simone Veil, University Versailles Saint Quentin.

The inclusion number will be used to identify the sample, no identifying data will be transferred to the laboratory.

Once all analysis for this trial has been completed, all blood samples will be destroyed.

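### The only dry-blood-spot endpoint is a correlation with serum, which cannot show proportional bias; the paired venous whole-blood aliquot has no stated storage, assay or analysis

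*Protocol*

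**What the plan says.** Protocol section 3.2 sets the objective: "To determine the feasibility of measuring tranexamic acid in dry blood spots". The endpoint attached to it, in section 4.1.2 and repeated in the Summary, is "Correlation between serum and dry blood spot concentrations for each administration route at visits V1, V3, V5". No other spot endpoint is given.

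Section 5.7 (subsection on the pharmacokinetics study, numbered 5.8.1) describes the samples. At one time-point in each of V1, V3 and V5, between 5 minutes and 8 hours after dosing, "a capillary blood sample will be taken at a finger with a lancet and a drop of blood will be placed on Mitra" (the sampling device). It continues: "An aliquot of 200µL of whole blood will be taken and aliquoted from the venous blood sample taken at the same time". For the venous samples, "each dosage requires 0,5 ml of blood in dry tube without anticoagulant".

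Storage is given for serum (frozen at -20°C) and for the spots: "The filter papers will be kept at ambient temperature in the Clinical Investigation Centre of Necker Hospital during the study period". None is given for the whole-blood aliquot. The same section says that all blood samples will be destroyed once the trial's analyses are complete.

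Section 8.1 says that tranexamic acid will be measured in samples by liquid chromatography with mass spectrometry, without naming the matrix. Section 12 contains no spot analysis. The full blood count ("Haematology tests (full blood count" in the V6 list of section 5.3, and also at V0) goes into the safety tables of section 12.1. It is not linked to the spots.

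**The concern.** Two features of the endpoint limit what it can show.

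First, it is a correlation. That measures how closely the points follow a straight line, not whether the two measurements agree. A device that reads a constant percentage low or high leaves r unchanged.

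Second, the comparator is a different matrix. The spot/serum ratio is the product of the blood-to-serum ratio, the device factor and any capillary-venous difference. Serum alone cannot say which of these is responsible for a shortfall.

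The sample that would remove the matrix effect is already being drawn, at the same moment as each spot, but the protocol gives it no purpose. If the aliquot is not assayed, it will be destroyed with the rest and the comparison cannot be recovered. What is at stake is the answer to the feasibility question. The primary pharmacokinetic endpoint and the safety endpoints are not affected.

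**Working it through.** The protocol gives no sample-size or precision figure for the spot endpoint, so there is none to reproduce. The statement in section 12.2 (15 volunteers, relative standard errors below 30%) concerns the pharmacokinetic parameters only.

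**Inputs from the protocol.** 15 volunteers, three dosing visits, one spot and one aliquot per visit: 15 pairs per route and 15 x 3 = 45 in total.

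**Inputs assumed, because the protocol does not give them.** Haematocrit H from 0.36 to 0.50; red-cell/serum partition k from 0 (no uptake) to 1 (full equilibration); device-and-capillary factor b; serum concentrations log-uniform from 2 to 60 mg/L; random error with SD 0.10 on the log scale.

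**Step 1: size of the matrix effect.** Blood/serum = (1 - H) + H x k.
- k = 0: 0.64 at H = 0.36, 0.57 at H = 0.43, 0.50 at H = 0.50.
- k = 0.5, H = 0.43: 0.57 + 0.215 = 0.785.
- k = 1: 1.00 at any H.

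The ratio can therefore lie anywhere from about 0.50 to 1.00, and the effect may be nil.

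**Step 2: what the correlation can detect.** Model: spot = serum x [(1 - H) + H x k] x b x error. For any b > 0, corr(serum, b x spot) = corr(serum, spot). In 4,000 simulated sets of 15 pairs, with H uniform over its range and k = 0:

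| b | mean r | spot/serum | spot/whole blood |
|---|---|---|---|
| 0.7 | 0.987 | 0.40 | 0.70 |
| 1.0 | 0.987 | 0.57 | 1.00 |
| 1.3 | 0.987 | 0.74 | 1.30 |

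A 30% proportional error in either direction does not move r.

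**Step 3: what the spot/serum ratio adds, and where it stops.** Three different situations give the same ratio:

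| k | b | mean r | spot/serum | spot/whole blood |
|---|---|---|---|---|
| 0 | 1.00 | 0.987 | 0.57 | 1.00 |
| 0.5 | 0.727 | 0.991 | 0.57 | 0.727 |
| 1 | 0.57 | 0.991 | 0.57 | 0.57 |

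At H = 0.43 the products are 0.57 x 1.00 = 0.57, 0.785 x 0.727 = 0.57 and 1.00 x 0.57 = 0.57. Neither r nor spot/serum tells an accurate device from one reading 43% low. The spot/whole-blood ratio does.

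**Step 4: precision.** With n = 15 per route, an observed r of 0.95 has a Fisher-z 95% interval of tanh(1.832 ± 1.96/√12) = 0.85 to 0.98.

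**The case against.** The best case for the plan is that serum is the matrix of the primary endpoint, so whether spots track serum is the practical question, and the objective is feasibility rather than device validation. The analysis plan or a laboratory plan, neither of which is shown, may well assay the aliquot. This stands in part. It is a reason to keep the serum correlation and to rate the point as minor. It does not change the fact that the protocol itself fixes a correlation with serum as the sole spot endpoint.

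Four stronger readings are tempting, and the documents do not support them.

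- *Device error cannot be separated from the blood-to-serum ratio in this trial.* That is true of the endpoint as written, not of the material collected. Assaying the aliquot removes the matrix effect. Even then, the spot is finger-prick blood and the aliquot is venous, so any capillary-venous difference stays mixed with device error.
- *A poor correlation could be haematocrit mistaken for device failure.* In the worst assumed case the ratio varies 0.64/0.50 = 1.28-fold between volunteers, yet mean r is still 0.987 over the assumed concentration range. The risk is a high r that hides bias.
- *The full blood count is used nowhere, and haematocrit should convert spots to serum.* Haematology is tabulated for safety; it is unused only for the spot question. Haematocrit is never named, and counts are taken at V0 and V6, not on the spot days V1, V3 and V5, while dosing may span three months. A conversion should not rest on it.
- *No spot-to-serum factor can be obtained.* A correlation coefficient gives none, but the paired spot and serum values do, as a ratio or regression.

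**Conclusion.** The point holds as a minor one. As written, the sole spot endpoint cannot show proportional bias, and its serum comparator mixes the blood-to-serum ratio with device and capillary-venous error. The simultaneous whole-blood aliquot, up to 45 in all, has no stated storage, assay or analysis.

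That r is unaffected by a proportional error is exact and rests on no assumption. The size of the matrix effect is unknown: blood/serum from about 0.50 to 1.0, resting on assumed haematocrit and red-cell uptake. The values of r near 0.99 also depend on the assumed concentration range and 10% error.

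**What to change.** - **Section 5.7:** state how the whole-blood aliquot is handled, stored and assayed. The venous tube contains no anticoagulant, so handling before storage needs stating too.
- **Sections 4.1.2 and 12.1:** keep the serum-spot correlation as planned, reported unadjusted. Add (a) the spot/venous whole-blood ratio with 95% limits of agreement, noting that it still includes any capillary-venous difference; and (b) the spot/serum and whole-blood/serum ratios with 95% limits. Where routes are pooled, allow for up to three pairs per volunteer.
- **Haematocrit:** any relation to it is exploratory only, because counts are taken at V0 and V6.

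The cost is up to 45 further assays on blood already drawn, and a short analysis. Some whole-blood assay validation may also be needed, since the two tranexamic acid assays cited in section 8.1 are, by their titles, for serum and plasma. No new blood draw or visit is required.

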4.2 Research methodology

4.2.1 Design of the trial

This research study is a phase I/II, single-centre, prospective, randomised, cross-over trial in healthy volunteers.

The design will be as follows:

The volunteers will be randomized into each of the 6 treatment groups (2-3 patients per group). The volunteers will receive tranexamic acid through the intravenous, intramuscular or oral route, in 6 different orders depending of the group, on three separate days (see Figure 1). The order used for the different routes of administration in each volunteer is not a factor that could influence the results of this pharmacokinetic study. Nevertheless, in order to reflect the best of all the variability that could be introduced into the system, the design selected for the study includes the 6 possible groups with regard to the sequence of routes of administration. Since the planned number of volunteers is 15, the groups consist of 2 or 3 volunteers alternately. This will not affect the final analysis, since the different groups will not be compared with each other, only the 3 routes of administration (oral, intravenous and

intramuscular) will be compared, each with a total of 15 patients. Any randomized participant who has not received all three drug doses will be replaced and the replacement will be allocated to the same randomisation group.

[figure not shown]

Figure 1: *Overview of randomisation groups*

4.2.2 Number of participating sites

This research is a single centre study which will take place at the Clinical Investigation Centre of Necker Hospital, Paris, France.

4.2.3 Identification of the participants

At inclusion the investigator will assign the patient an inclusion number as follows:

- the first three digits correspond to the centre number, e.g. 001 to 999
- the following four digits correspond to the patient sequential entry number (for example, the third patient screened in centre 001 will be patient 001 0003). The participants will be identified by their inclusion number and initials (participant last and first name initials) for the entire duration of the trial.

4.2.4 Randomisation

Randomisation will be done centrally by using a web-based access to the randomisation system which will be provided by AP-HP. Volunteers will be randomized into each of 6 treatment groups (2-3 patients per group). See section 4.2.1 for overview of treatment groups.

5 PROCEDURE FOR THE TRIAL

Before any examination or intervention may be carried out for the trial, the investigator must obtain the *free, informed and written consent of the participant*.

Participants in the clinical studies described in article L.1121-1(1° paragraph) of the Code de la Santé Publique are eligible for prior medical examination appropriate for the trial.

All visits (except End of Study visit which is telephone follow-up) will take place at Clinical Investigation Centre, Necker Hospital, Paris.

5.1 Screening visit (V0)

Healthy volunteers will be recruited by advertisement in universities or website to the general public.

A first contact by phone or mail with healthy volunteer who wants to participate will be done by investigator in order to verify main eligibility criteria and give information about the study.

If volunteer agrees to consider participation, an appointment for screening visit will be scheduled.

The screening visit will take place between 1 and 7 days before the inclusion visit.

During the screening visit (V0):

Consent: Informed consent must be signed by the participant before any research activity is carried out. An investigator trained on the trial Protocol will provide full information to the participant and will answer all questions the participant may have regarding the study. Once the participant has had all of their questions answered and are willing to proceed, their written consent will be obtained. The participant will be given a copy of the written consent to keep.

Whose consent must be obtained?	Who informs the individual and collects their consent?	When is the individual informed?	When is the individual's consent taken?
The trial participant	The investigator trained on the trial protocol	By mail or phone before screening visit (at the latest when taking appointment for screening visit)	At screening visit

Eligibility assessments:

- Demographic data (including ethnic origin) will be collected. It is necessary to collect information on ethnic origin because this is known to have an impact on the glomerular filtration rate, which could modify the drug pharmacokinetics of tranexamic acid, as it is eliminated 100% by the kidneys.
- Medical History and concomitant treatment are collected to assess eligibility.
- Following Examinations will be performed:
 - **Physical examination** including **weight and height**
 - **Vital signs** (including Blood pressure, heart rate, respiratory rate)
 - **Laboratory tests:**
 - Haematology tests (full blood count)
 - Renal function test (urea, creatinine and GFR calculated according to the CKD-EPI formula [36])
 - Coagulation tests (fibrinogen, D-dimers, prothrombin time and partial thromboplastin time)
 - For women: pregnancy test (urine β hCG)

5.2 Inclusion visit (V1)

All **inclusion and exclusion criteria** have to be checked by physician, to ensure laboratory tests done at the screening visit are within normal values and for women, the pregnancy test is negative.

If a volunteer meets all inclusion and has no exclusion criteria and s/he consents to participate, the participant is considered **enrolled**. The investigator will randomize her/him to one of six groups (see Section 4.2.1).

Visit V1 (=1st drug administration):

- All women must have a **pregnancy test** (urine β hCG) done which must be negative to continue this visit.
- Participants medical history will be checked to ensure there are no changes since V0 visit.
- Baseline blood pressure, heart rate and respiratory rate will be recorded
- T₋₁: One blood sample will be taken for pharmacokinetics immediately prior to drug administration (0,5 mL venous blood taken in a dry tube without anti-coagulant)

- T₀: Drug Administration (PO, IV or IM) (as per randomization)
- **Pain assessment** using a Visual Analogue Scale (VAS) will be recorded immediately after drug administration and at 2 hourly intervals up to 8 hours. The VAS used will be the Numerical Pain Rating Scale where individuals rate their pain on a ten-point numerical scale. The scale is composed of 0 (no pain at all) to 9 (worst imaginable pain). The duration of any pain associated with IV or IM administration will be assessed once at 8 hours. Participants will be offered pain relief if needed in the form of simple analgesia (paracetamol).
The duration of any pain associated with IV or IM administration will be assessed once at 8 hours.
- Blood samples for **pharmacokinetics** (*0,5 mL of venous blood in dry tube without anti-coagulant*) will be taken at the following times after drug administration:
 - T₀+ 5min (only for IV route)
 - T₀+30min
 - T₀+1h
 - T₀+2h
 - T₀+3h
 - T₀+4h
 - T₀+5h
 - T₀+6h
 - T₀+8h (only for IM and PO routes)
- **Dry Blood Spot:** At one time-point (any time-point between T₀+ 5min and T₀+8h), a capillary blood sample will be taken at a finger with a lancet and a drop of blood will be placed on Mitra[®] device. An aliquot of 200µL of whole blood will be taken and aliquoted from the venous blood sample taken at the same time.
- **Reaction at site of injection:** Each injection site will be checked visually for local reaction and any other complications (including redness, swelling, induration, tenderness, ecchymosis, necrosis, nerve injury, infection) every fifteen minutes after administration for the first one hour then every two hours up to 8 hours after each injection and once at each subsequent visit. Reaction will be measured in millimetre, and time of occurrence will be recorded.

- Participants will have their **vital signs** (blood pressure, heart rate and respiratory rate) monitored and recorded at every fifteen minutes after administration for the first one hour then every two hours after drug administration.
- All **adverse events** and **concomitant treatments** will be recorded. The following adverse events will be elicited specifically (fever, nausea, vomiting, diarrhoea, visual impairment, seizure).

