2.5 Name and description of the investigational medicinal product(s)

Patient will receive the marketed forms of tranexamic acid:

- Exacyl® (Sanofi Aventis) 0.5 g/5 ml injectable solution
- Exacyl® (Sanofi Aventis) 1 g/10 ml oral solution.

See Section 7 for further information about the product.

2.6 Description and justification of the dosage, route of administration, administration schedule and treatment duration

Each volunteer will receive one dose of medication through each of the three routes (oral, intravenous, intramuscular), on three separate days. The selected doses are 1g for the intravenous and intramuscular routes and 2g for the oral route due to the 100% intramuscular bioavailability and 50% oral bioavailability [10].

See Section 7 for further information about the administration of the product.

2.7 Summary of the known and foreseeable benefits and risks for the study participants

There is no benefit for participants. The foreseeable risks are those related to IMP and the routes of administration. The most frequent risks associated with the administration of tranexamic acid through the intravenous, intramuscular and oral routes are:

- digestive disorders (diarrhoea, nausea, vomiting; appearing in >1/100 and <1/10 patients)
- allergic dermatitis (>1/1000 and <1/100)

Cases of visual impairment or convulsions have been reported with tranexamic acid, but only at high doses or during cardiac surgery. In the present study, the doses (1g through the parenteral routes and 2g through the oral route) are lower than doses used in routine clinical practice.

Insertion of intravenous cannula for intravenous administration of TXA and blood sampling may cause pain (common), bruising (rare), local allergic reaction secondary to disinfectant or adhesive plaster, vagal malaise and possibly infection (very rare).

Intramuscular injection procedure of a large volume may cause pain (common), Local reaction at site of injection (including Injection site redness (common), Injection site swelling (common), Injection site tenderness (common), Injection site ecchymosis (common), Injection site induration (rare), injection site necrosis (very rare), injection site nerve injury

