10 SAFETY ASSESSMENT - RISKS AND RESTRICTIONS ADDED BY THE STUDY

10.1 Safety endpoints

Safety Endpoints are:

- ✓ Number of participants with solicited local and systemic adverse events.
- ✓ Average pain score reported by participants during intramuscular administration (visual analogic scale)
- ✓ Duration of pain from intramuscular administration (hours)
- ✓ Local reaction at site of injection (redness, swelling, induration, tenderness, ecchymosis, necrosis, nerve injury, infection)
- ✓ Systemic events (fever, nausea, vomiting, seizure, diarrhoea, visual impairment)
- ✓ Vital signs (blood pressure, heart rate and respiratory rate) after administration

Number of participants reporting one or more adverse events and serious adverse events

10.2 Anticipated methods and timetable for measuring, collecting and analysing the safety endpoints

Safety Endpoints are recorded at each visit: for more details see sections 5.2 and 5.3.

- ✓ Pain is assessed by Visual Analog Scale (intensity from 0 to 9)
- ✓ Reaction at site of injection is assessed by visual inspection (measure in mm of the surface in case of reaction, and time of occurrence)

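### The 0–9 pain score is not tied to the administration site and has no pre-dose value, so scores reported by route can include pain from other sources

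*Protocol*

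**What the plan says.** Section 5.2, repeated for later visits in section 5.3, has volunteers score pain from 0 to 9 on a "Numerical Pain Rating Scale where individuals rate their pain on a ten-point numerical scale". On dosing days the score "will be recorded immediately after drug administration and at 2 hourly intervals up to 8 hours". It is taken again at 24 hours (V2, V4, V6). It is collected on all three dosing days, including the oral one. Baseline blood pressure, heart rate and respiratory rate are listed before dosing, but a baseline pain score is not.

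The companion item is worded differently: "The duration of any pain associated with IV or IM administration will be assessed once at 8 hours".

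The endpoint appears in two forms:
- Section 4.1.2: "Average pain score and duration of pain after administration (visual analogue scale) for each administration route at visits V1, V3, V5".
- Section 10.1: "Average pain score reported by participants during intramuscular administration (visual analogic scale") and "Duration of pain from intramuscular administration (hours").

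On other sources of pain, section 2.7 states: "Insertion of intravenous cannula for intravenous administration of TXA and blood sampling may cause pain (common"). Sections 5.2 and 5.3 add, once on each dosing day, that "a capillary blood sample will be taken at a finger with a lancet" at any time-point from 5 minutes to 8 hours. Section 5.3 sets the wash-out at 48 hours or more. Section 12.1 summarises pain scores in tables of mean, median, standard deviation and range.

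**The concern.** The score as worded covers all of a volunteer's pain, while the endpoints present it as pain from a route of administration. The duration item shows that the authors could limit a pain question to the administration, so its absence from the intensity question is a gap in the measurement.

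The scope given in the protocol summary includes assessing the safety of IM administration, and section 2.7 names local tissue reaction as a concern with that route. A route mean that mixes injection pain with needle, cannula or lancet pain overstates the pain of the route. It can also produce a non-zero score for the oral route, which has no injection site. Without a pre-dose value, soreness carried over from an earlier injection would be credited to the next route. An analysis plan cannot undo this, because the components are never recorded separately.

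**Working it through.** **1. The sections side by side**

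| Place | Routes | What is measured |
|---|---|---|
| 4.1.2 | each route | score and duration after administration, V1, V3, V5 |
| 5.2–5.3, score | all dosing days | the volunteer's pain, no site or cause, to 8 h and at 24 h |
| 5.2–5.3, duration | IV or IM | pain associated with the administration |
| 10.1 | IM only | score during administration; duration of pain from it |

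The sections disagree on routes, on attribution, and on timing (during or after).

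**2. Procedural load per dosing day, counted from section 5.2**

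- IV: pre-dose, 5 min, 30 min, 1, 2, 3, 4, 5, 6 h = 1 + 8 = 9 venous samples.
- IM and oral: pre-dose, 30 min, 1, 2, 3, 4, 5, 6, 8 h = 1 + 8 = 9 venous samples.
- One lancet on each day.

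This agrees with the chronology table in section 5.5 (one pre-dose and eight post-dose samples). The load is nearly equal by route. Two differences remain: the 8 h score coincides with a sample on IM and oral days but not on IV days, and the lancet time is free.

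**3. Effect on the paired IM–IV difference**

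The protocol gives no pain values, so all inputs here are assumptions: mean site pain IM/IV of 4/2, 3/1 or 2/1 with SD 1.5; procedural pain with the same mean (1, 2 or 3) and SD 1 on both days; all drawn independently, not below 0; scores rounded and limited to 0–9; 200,000 simulated pairs.

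With site pain S and procedural pain P, the score is S + P if pains add, or max(S, P) if volunteers report their worst pain. Without rounding and limits, the additive case cancels on average: (S_IM + P) − (S_IV + P) = S_IM − S_IV.

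| Site pain IM/IV | Difference with P = 0 | Mean P | Pains add | Worst pain |
|---|---|---|---|---|
| 4/2 | about 1.94 | 1 | 1.93 (99%) | 1.71 (88%) |
| 4/2 | | 2 | 1.90 (98%) | 1.40 (72%) |
| 4/2 | | 3 | 1.83 (94%) | 1.00 (51%) |
| 3/1 | about 1.80 | 1 | 1.79 (100%) | 1.40 (78%) |
| 3/1 | | 2 | 1.78 (99%) | 1.00 (56%) |
| 3/1 | | 3 | 1.75 (98%) | 0.60 (33%) |
| 2/1 | about 0.84 | 1 | 0.84 (100%) | 0.59 (71%) |
| 2/1 | | 2 | 0.84 (100%) | 0.40 (47%) |
| 2/1 | | 3 | 0.83 (99%) | 0.20 (24%) |

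The 95% confidence half-width at n = 15 is 2.145 × SD_d / √15. For 4/2 with P = 0 it is 2.145 × 2.08 / 3.873 = 1.15. For 4/2 with mean P = 1 and pains adding it is 2.145 × 2.40 / 3.873 = 1.33. Over all additive cases it grows from 1.03–1.15 to 1.24–1.35 points.

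**4. Leftover soreness**

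Of the six sequences, three have IM before IV. Section 4.2.1 puts 2 or 3 volunteers alternately in each group: 3 × 2 + 3 × 3 = 15. Those three sequences therefore hold 6 to 9 volunteers. If each still had 1 point of IM soreness on the IV day (an assumption) and pains add, the IV mean rises by 6/15 = 0.4 to 9/15 = 0.6 points, and the IM–IV difference falls by as much. Whether soreness lasts that long is unknown. The score as planned could not show it.

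**The case against.** A reader might infer that the score hides how IM compares with IV. The documents do not support that. Each volunteer receives all three routes with the same number of samples and lancets on each dosing day, so common procedural pain largely cancels within person if pains add, and the oral day indicates the background. A ratio of route means would shrink under added background, but section 12.1 plans no ratio and states no IM–IV test.

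Other points on this side also stand:
- The cannula is described as serving sampling too, so nine samples need not be nine needle sticks.
- On IM and oral days the first score precedes every post-dose sample and the lancet, so it is the least affected.
- On the IV day the dosing cannula is arguably part of that route's own pain.
- Tenderness is checked at each injection site every 15 minutes for an hour, then two-hourly to 8 hours and at subsequent visits, so local tolerance does not rest on this score alone.
- The wording on the pain form is not in the protocol and may be narrower.

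A reader might also infer that the two IM injections need separate scores. One score can properly describe the pain of the whole IM dose, so separate scores are a preference.

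What this leaves untouched is that the tabulated absolute scores carry any procedural pain. Cancellation depends on how volunteers combine pains, which the protocol does not say, and it does not cover leftover soreness. The sections also disagree on what is measured.

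**Conclusion.** The concern holds as a defect of measurement and consistency in a secondary endpoint. The intensity score is not anchored to the administration, has no pre-dose value, and is described differently in sections 4.1.2, 5.2–5.3 and 10.1. Absolute scores by route, including the oral route, may be too high by an amount the documents do not allow anyone to estimate.

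For the IM–IV difference the fair statement is possible dilution: little bias if pains add (94–100% retained, with a somewhat wider interval), and 24–88% retained if worst pain is reported. These figures rest entirely on assumed pain levels, equal mean procedural pain on both days and independence between days. Leftover soreness is a further possibility that the documents neither establish nor exclude. The primary pharmacokinetic endpoint and the sample size are unaffected. The change is worth making before data collection, because it cannot be recovered afterwards.

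**What to change.** - In sections 5.2 and 5.3, word the 0–9 score as pain at the site of, or due to, the study drug administration, and state whether insertion of the dosing cannula counts towards the IV score.
- Add a pain score before dosing at V1, V3 and V5, alongside the baseline vital signs already listed, so that pain already present can be seen.
- Record sampling or cannula-site pain as a separate item on all three dosing days, with the oral-day scores serving as background.
- Reconcile sections 4.1.2, 5.2–5.3 and 10.1 on what the score and the duration measure, when, and for which routes.

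The cost is one or two extra lines on the existing pain form and a short rating before each dose. No visit or procedure is added.
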